4. SUBJECT DISPOSITION

4.1. Subject Enrollment and Disposition

Key study dates (first subject visit, first subject randomized, last subject randomized, last subject last visit) will be provided.

A summary of subject enrollment will be provided by treatment group for each country and overall. The summary will present the number and percentage of subjects enrolled. For each column, the denominator for the percentage calculation will be the total number of subjects with none missing value for that column.

Subject screening, screening failures and detailed reasons for screening failures will be summarized. Screening will be defined as all subjects who signed informed consent and reasons for screening failure will be summarized by inclusion or exclusion criteria.

A similar enrollment table will be provided by randomization stratum. The denominator for the percentage of subjects in the stratum will be the total number of enrolled subjects. If there are discrepancies in the value used for stratification assignment between the IRT and the clinical database, the value collected in the clinical database will be used for the summary. A listing of subjects with discrepancies in the value used for stratification assignment between the IRT and the clinical database at the time of data finalization will be provided.

The randomization schedule used for the study will be provided as an appendix to the CSR.

A summary of subject disposition will be provided by treatment group. This summary will present the number of subjects who signed informed consent, the number of subjects randomized, the number of subjects randomized and treated, and the number of subjects in each of the categories listed below:

- ITT population
- SAF population
- MITT population
- Micro-MITT population
- CR-MITT population
- Extend the micro-MITT population
- CE population
- ME population
- PK population
- Completed treatment
- Discontinued treatment and Primary reason for treatment discontinuation
- Completed study

- Discontinued study and Primary reason for study discontinuation

For the primary reason of treatment and study discontinuation, the number and percentage of subjects in each category will be provided. The denominator for the percentage calculation will be the total number of subjects in the Safety population corresponding to that column.

The following by-subject listings will be provided by subject identification (ID) number in ascending order to support the above summary tables:

- Primary reasons for treatment and study discontinuation
- Reasons for not randomization (will be provided by screening ID number in ascending order)
- Lot number and kit ID

4.2. Protocol Deviations

Subjects who did not meet the eligibility criteria for study entry but enrolled in the study, will be summarized regardless of whether they were exempted by the sponsor or not. The summary will present the number and percentage of subjects who did not meet at least 1 eligibility criterion and the number of subjects who did not meet specific criteria by treatment group based on the ITT population. A by-subject listing will be provided for those subjects who did not meet at least 1 eligibility (inclusion or exclusion) criterion.

Protocol deviations occurring after subjects entered the study are documented during routine monitoring. The number and percentage of subjects with important protocol deviations by deviation reason (e.g., nonadherence to study drug, violation of select inclusion/exclusion criteria) will be summarized by treatment group for the ITT population. A by-subject listing will be provided for those subjects with important protocol deviation.

5. BASELINE CHARACTERIZATION

5.1. Demographics Baseline Characterization

Subject demographic variables (i.e., age [as a continuous variable, categorized as <65 years and \geq 65 years], sex, race, and ethnicity) and baseline characteristics (weight [in kilograms], height [in centimeters], and body mass index [in kilograms per meter²]) were summarized by treatment group. Overall, summarization will be done using descriptive statistics for continuous variables and subject cases and percentages for categorical variables. Demographic data will be summarized based on safety and micro-MITT populations.

A list of subject demographics is provided in ascending order of subject number and includes the date of informed consent signing.

5.2. Other Baseline Characteristics Analysis

Other baseline characteristics include:

- Country/region (China and the rest of the world)
- Type of infection at baseline (non-ventilated HABP, mechanically ventilated HABP, VABP)
- APACHE II score (continuous variable)
- APACHE II scores (<10, 10 to <15 and \geq 15)
- Sequential Organ Failure Assessment (SOFA) score
- Glasgow Coma Scale (GCS) score (continuous variable)
- Glasgow Coma Scale (GCS) score (<7 and \geq 7)
- Baseline ICU admission (yes/no/missing), i.e., ICU admission at the time of the first dose; if the ICU admission time is missing, the admission time is filled in using 00:00, and the ICU departure time is filled in using 23:59
- Baseline eGFR (continuous variable)
- Baseline eGFR (<30 mL/min, 30 to <60 mL/min, 60 to <90 mL/min, 90 to <150 mL/min, 150 to < 250 mL/min and \geq 250 mL/min)
- Baseline Liver Function (Normal, Abnormal), Abnormal liver function was defined as subjects with baseline results of any of the ALT, AST, ALP and total bilirubin in laboratory tests that were outside the normal range of values.
- Received antimicrobial therapy for this HABP/VABP (yes/no)
- Whether the subject received systemic or inhaled effective gram-negative antimicrobial medication for more than 24 hours sustained against a specific infection of HABP/VABP within 72 hours prior to randomization (Yes/No)
 - Whether the subject's previous antibiotic treatment was considered a clinical failure (yes/no), only if the answer to the above question was "yes".

- Whether the subject required mechanical ventilation because of treatment failure (yes/no), only if the answer to the above question was "yes".
- Baseline lower respiratory tract gram-negative infections (no; yes: mono/poly)
- Top 5 ranking of respiratory pathogens in the lower respiratory tract at baseline HABP/VABP (5 most frequent in total groups)
- Resistance to gram-negative pathogenic bacteria of the respiratory tract at baseline (carbapenem-resistant/non-resistant)
- Concomitant bacteremia at baseline (yes/no)

These baseline characteristics will be summarized by test drug group, control drug group, and aggregate, using descriptive statistics for continuous variables and number and percentage of subjects for categorical variables. These baseline characteristics will be summarized based on the safety population and the micro-MITT population.

Also, baseline pathogens for the micro-MITT, extended micro-MITT, and CR-MITT populations will be summarized, as well as MIC results for IMI-XNW4107 and IMI/REL for these baseline pathogens. In this analysis, the MIC results for IMI-XNW4107 and IMI/REL for each baseline pathogen will be presented separately in the corresponding treatment groups, and the number of subject cases infected with the specific pathogen will be calculated, as well as the corresponding MIC₅₀, MIC₉₀, and MIC ranges. MIC₅₀ and MIC₍₉₀₎ will be defined as being no less than 50% of the data and 90% of the data, respectively of the minimum value; MIC₅₀ and MIC₉₀ were calculated only if the number of subjects infected with a specific pathogen was 10 or more.

The rules for the processing and derivation of microbiological data, as well as related definitions, are detailed in Section [3.6.2](#).

Provides a list of other baseline characteristics of the subject, in ascending order of subject number.

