11. Subject is receiving hemodialysis or peritoneal dialysis or micro-dialysis or continuous venovenous hemofiltration or continuous venovenous hemodialysis.
12. Subject is anticipated to be treated with any of the following medications during the course of study therapy:
 - a. Valproic acid or divalproex sodium (or has used valproic acid or divalproex sodium in the 2 weeks prior to screening)

- 
- b. Concomitant systemic (IV or oral) Gram-negative antibacterial agents in addition to those designated in the study treatment groups
 - c. Concomitant systemic (IV or oral) antifungal or antiviral therapy for the index infection of HABP/VABP.
13. Life expectancy is <3 days.
 14. Subjects in refractory septic shock, defined as persistent hypotension despite adequate fluid resuscitation and vasopressive therapy at the time of randomization.
 15. Subjects with 1 or more of the following laboratory abnormalities in baseline specimens: aspartate aminotransferase, alanine aminotransferase $>3 \times$ the upper limit of normal (ULN), total bilirubin level $>2 \times$ ULN (except for isolated hyperbilirubinemia due to known Gilbert's disease), neutrophils <500 cells/mm³, platelet count $<40,000$ /mm³.
 16. History of active liver disease or cirrhosis.
 17. Subjects with an APACHE II score of >30 .
 18. A female who is pregnant or breastfeeding or has a positive pregnancy test as screening.
 19. Subject is participating in any clinical study of any investigational medication (i.e., non-licensed medication) during the 30 days prior to randomization. COVID-19 vaccines that are given under emergency use authorization are not considered investigational agents.
 20. Any other condition or prior therapy, which, in the opinion of the investigator, would make the subject unsuitable for this study.

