7.6.2. Clinical Laboratory Evaluations

All Screening laboratory tests will be performed locally to assess study eligibility. The list of required local laboratory tests is in [Appendix 1](#). Baseline and post-baseline safety laboratory tests will also be performed locally. The timepoints at which these samples will be collected are shown in the Schedule of Assessments ([Table 9](#))

The total volume to be drawn in the study may vary based on local/regional specific laboratory requirements.

A full list of laboratory parameters is provided in [Appendix 1](#).

The investigator will record on the laboratory report his/her medical opinion of the clinical significance of all laboratory values that are outside the laboratory reference range. The investigator will sign and date each laboratory report form. Clinically significant laboratory findings made after the start of study medication that meet the definition of an AE must be recorded on the eCRF (see Section [7.6.1.1](#) and Section [7.6.1.4.2](#)).

The investigator will provide the Sponsor or Sponsor's designee with a copy of each laboratory's certification and a tabulation of the normal ranges.

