8.1.2.4. Subgroup Analysis

Day 14 all-cause mortality will be analyzed in the MITT population for the following subgroups

- Age (< 65 and \geq 65)
- Gender (male and female)
- Country/region (China and the rest of the world)
- Type of infection at baseline (non-ventilated HABP and ventilated HABP)
- Baseline APACHE II scores (<15 and \geq 15)
- ICU admission at baseline (yes/no)
- Baseline eGRF classification (<30 mL/min, 30 to <60 mL/min, 60 to <90 mL/min, 90 to <150 mL/min, 150 to <250 mL/min and \geq 250 mL/min)
- Baseline liver function (normal, abnormal)
- Received antimicrobial therapy for this HABP/VABP (yes/no)
- Whether the subject's prior antibiotic therapy was considered a clinical treatment failure (yes/no)
- Baseline lower respiratory tract gram-negative infections (mono/poly)

- Top 5 Ranking of Respiratory Gram-Negative Bacteria under Baseline HABP/VABP (5 most frequent in combined dose groups)
- Resistance to gram-negative pathogenic bacteria of the respiratory tract at baseline (carbapenem-resistant/non-resistant)
- Concomitant bacteremia at baseline (yes/no)

For a subject, if the value of the grouping variable cannot be determined, this subject will be excluded from the corresponding subgroup analysis. Non-stratified risk difference between treatment groups will be evaluated for each of the subgroups. A forest plot will graphically present the non-stratified risk difference and 95% CI using normal approximation with a continuity correction on the treatment differences in the all-cause mortality rates at Day 14 between IMI-XNW4107 and IMI/REL for each of the subgroups. For both treatment groups, subjects with unknown survival at Day 14 will not be considered dead.

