8.2.1.2. Subgroup Analysis of all-cause Mortality

All-cause mortality at Day 28 will be analyzed in the MITT population in subgroups similar to those described in Section 8.1.2.4.

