9.1.6.2. Subgroup analysis of treatment-emergent adverse events

The incidence of TEAE and deaths mentioned in Section 9.1.6.1 will be summarized in the safety population in a manner similar to that described in Section 8.1.2.4 and analyzed by the following subgroups.

- Age (< 65 years and \geq 65 years)
- Gender (male and female)
- Region (China and the rest of the world)
- Type of infection at baseline (non-ventilated HABP and ventilated HABP)
- Baseline APACHE II total score (<15 and \geq 15)
- Baseline eGRF (<30 mL/min, 30 to <60 mL/min, 60 to <90 mL/min, 90 to <150 mL/min, 150 to < 250 mL/min and \geq 250 mL/min)
- Baseline liver function (abnormal and normal)

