9.2.3. Liver-related Laboratory Evaluations

Liver-related abnormalities after initial study drug dosing will be examined and summarized using the number and percentage of subjects who were reported to have the following laboratory test values for postbaseline measurements:

- Aspartate aminotransferase (AST): (a) > 3 times of the upper limit of reference range (ULN); (b) > 5 x ULN; (c) > 10 x ULN; (d) > 20 x ULN
- Alanine aminotransferase (ALT): (a) > 3 x ULN; (b) > 5 x ULN; (c) > 10 x ULN; (d) > 20 x ULN
- AST or ALT: (a) > 3 x ULN; (b) > 5 x ULN; (c) > 10 x ULN; (d) > 20 x ULN
- Total bilirubin: > 2 x ULN
- Alkaline phosphatase (ALP) > 1.5 x ULN
- AST or ALT > 3 x ULN and total bilirubin: (a) > 1.5 x ULN; (b) > 2 x ULN

For individual laboratory tests, subjects will be counted once based on the most severe postbaseline values. For both the composite endpoint of AST or ALT and total bilirubin, subjects will be counted once when the criteria are met at the same postbaseline visit date. The denominator is the number of subjects in the Safety Analysis Set who have no missing postbaseline values of all relevant tests at the same postbaseline visit date. A listing of subjects who met at least 1 of the above criteria will be provided.

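### The SAP's baseline class of abnormal liver function also captures values below the lower limit of normal, unlike the documents' liver-specific criteria; the effect is confined to the baseline table and descriptive subgroups

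*SAP*

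**What the plan says.** SAP 5.2 lists baseline liver function as a two-level characteristic, normal or abnormal. Abnormal rests on "baseline results of any of the ALT, AST, ALP and total bilirubin in laboratory tests that were outside the normal range of values". No multiple of a limit and no direction is given, and nothing elsewhere in either document narrows it.

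The class is then reused:

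- SAP 8.1.2.4 names it as a subgroup factor for Day 14 mortality in the MITT population. On method it says: "Non-stratified risk difference between treatment groups will be evaluated for each of the subgroups".
- SAP 8.2.1.2 carries the list over to Day 28: "All-cause mortality at Day 28 will be analyzed in the MITT population in subgroups similar to those described in Section 8.1.2.4".
- SAP 8.2.2.2, 8.2.3.4 and 8.2.4.2 refer to the same list for clinical, microbiological and overall outcomes.
- SAP 9.1.6.2 names it again for TEAEs and deaths in the safety population.

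The reference ranges are those of the sites' own laboratories. Protocol 7.6.2 states: "Baseline and post-baseline safety laboratory tests will also be performed locally".

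**The concern.** A normal range has two ends. Protocol 7.6.1.4.2 treats it that way when it asks for a descriptor saying whether a result lies above or below it. A programmer who follows SAP 5.2 as written will therefore code a subject with one low value and nothing raised as abnormal. The documents' criteria written specifically about the liver use these same tests only in the upward direction.

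At stake is what the subgroup can tell a reader. It is the only efficacy and TEAE split by liver status in the SAP. Subjects with no raised value would be counted in its abnormal arm, which inflates the number reported there and pulls its estimates towards those of the normal group. Local ranges add a site effect: the same low result counts as abnormal where the laboratory prints a lower limit above zero, and as normal where it does not.

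**Working it through.** **Step 1: compare the directions.**

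- SAP 5.2, baseline class: ALT, AST, ALP, bilirubin; outside the range on either side.
- Protocol 4.2, exclusion criterion 15: AST or ALT above 3 x ULN, bilirubin above 2 x ULN; upper side only.
- Protocol 4.3.2, treatment discontinuation: ALT or AST at multiples of ULN, in some cases combined with bilirubin, INR or symptoms; upper side only for ALT, AST and bilirubin.
- SAP 9.2.3, post-baseline liver abnormalities: AST, ALT, bilirubin and ALP above multiples of ULN; upper side only.

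SAP 5.2 and SAP 9.2.3 use the same four tests with different directions, and no reason is given.

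**Step 2: can the number affected be derived?** No. The plan states no figure to reproduce. It gives no local ranges, no baseline distributions and no expected size for the class. What follows is illustration only.

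**Step 3: illustrative model.** The assumed inputs are:

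- h, the share of subjects with any of the four tests above ULN;
- q, the chance that one analyte is below its lower limit;
- k, the number of analytes with a lower limit above zero.

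Analytes are treated as independent. The planned 450 subjects (SAP 1.2) serve only as a scale.

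- Any low value: L = 1 - (1 - q)^k
- Low-only subjects, as a share of all: (1 - h) x L
- Low-only share of the abnormal class: s = (1 - h)L / [h + (1 - h)L]

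Results:

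| Case | h | q | k | L | Low-only of 450 | s |
|---|---|---|---|---|---|---|
| Low end | 60% | 1% | 1 | 0.010 | 0.40 x 0.010 x 450 = 2 | 0.004/0.604 = 0.7% |
| Mid | 40% | 2.5% | 2 | 0.049 | 0.60 x 0.049 x 450 = 13 | 0.030/0.430 = 7% |
| Mid | 30% | 2.5% | 2 | 0.049 | 315 x 0.049 = about 15 | 10% |
| Mid | 30% | 2.5% | 4 | 0.096 | 315 x 0.096 = about 30 | 18% |
| High end | 20% | 5% | 4 | 0.185 | 0.80 x 0.185 x 450 = 67 | 0.148/0.348 = 43% |

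An analyte with no lower limit above zero adds nothing. If that holds for all four, k = 0 and s = 0.

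**Step 4: what s does to the subgroup.** Suppose low-only subjects behave like the normal group and make up a similar share in both arms. The contrast between the abnormal and normal subgroups then shrinks by the factor 1 - s: to 0.93 of its value at s = 7%, 0.82 at 18%, and 0.57 at 43%.

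**Step 5: reach.** The primary analysis in SAP 8.1.2.1 stratifies by randomization factors, with country/region dropped under SAP 11. Liver function is not among them. Under SAP 3.7.3, baseline is the last non-missing result before the first dose, so the same pre-dose rule applies in both arms.

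**The case against.** Several points on the other side stand.

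- **Non-directional wording is not unique to SAP 5.2.** Protocol 7.6.2 has the investigator comment on any value beyond the reference range, and the shift tables in SAP 9.2.2 use normal and abnormal without direction. A reader might infer that every other rule in the documents counts only high values. That is too broad; it is true of the liver-specific criteria.
- **The documents do not state a purpose for the subgroup.** One might read it as a count of liver-impaired subjects, but the SAP speaks only of abnormal liver function.
- **The abnormal group is not necessarily mild.** A reader might infer this from criteria 15 and 16, the latter being "History of active liver disease or cirrhosis". But criterion 15 sets no cap on ALP and exempts isolated hyperbilirubinemia from Gilbert's disease.
- **An upper-limit rule is not specific either.** If each range is a central 95% range, 1 - 0.975^4 = 9.6% of subjects without liver disease also have at least one value above ULN. The fix leaves them in the class.
- **The impact is small.** The subgroups are descriptive estimates with no decision rule, and Protocol 8.7 makes the safety analyses descriptive. Baseline values are summarised (SAP 9.2.1) and laboratory results are listed by subject (SAP 9.2), so a reader could separate low values from high ones.

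These points limit the size and wording of the concern. They do not explain why a low enzyme or bilirubin value should define abnormal liver function here.

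**Conclusion.** The point holds as a minor correction. Read as written, SAP 5.2 classes subjects with only low values as abnormal, against the direction of the documents' own liver-specific criteria, and the class carries through to the baseline table and six sets of subgroup analyses.

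The number misplaced is unknown. The range of 0.7% to 43% of the abnormal group, with mid cases of about 7% to 18%, rests entirely on assumed values of h, q and k and on independence. None of these figures should be quoted as an estimate for this trial.

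A reader might go further and infer that the mortality comparison is biased or that the non-inferiority conclusion is at risk. The documents do not support either reading: the primary analysis does not use the variable, and the class is set from pre-dose results by one rule in both arms. The consequence is dilution and a less interpretable subgroup.

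**What to change.** In SAP 5.2, define abnormal as any of ALT, AST, ALP or total bilirubin above the upper limit of normal at baseline. Apply that class in 8.1.2.4, in 8.2.1.2, 8.2.2.2, 8.2.3.4 and 8.2.4.2, which refer to it, and in 9.1.6.2. Keep the label abnormal liver function, because a value above ULN is not proof of hepatic impairment.

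Make the change before unblinding. If the SAP is already final, SAP 1 provides for later changes to be documented in the CSR. The cost is one phrase and one line of code, with no new data.

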5.3. Medical History

For medical histories collected during the screening period.

Based on the safety population, the number and percentage of subjects with a medical history were provided, and the number of cases and percentage of subjects with a medical history were summarized according to System Organ Classification (SOC) and Preferred Terminology (PT).

Provide a list of the subject's past medical history in ascending order of subject number.

5.4. Prior Antibacterial Drug Therapy

Prior antibacterial drug therapy will be collected at screening.

A by-subject listing of prior antibacterial drug therapy will be provided by subject ID number in ascending order.

5.5. Prior Medications (Antibacterial and Others)

Prior medications (antibacterial and others) will be coded using the current version of the World Health Organization (WHO) Drug dictionary.

Prior medications (antibacterial and others) are defined as any medications taken before a subject took the first study drug. Prior medications were considered systemic gram-negative medications and included in the appropriate pooled analyses if their ATC codes appeared in the table below.

Table 5.5-1 Systemic Antimicrobial Medications Definitions

The figure is a Gantt chart with four columns. The first three columns are labeled 'ATC 2', 'ATC 3', and 'ATC 4' in bold black text at the top. The fourth column is labeled 'note' in brown text at the top. Each column contains several horizontal bars of varying lengths, representing different tasks or events. The 'note' column has a single, extremely long black bar that spans the entire width of the chart area.

Prior medications (antibacterial and others) will be summarized separately by Anatomical Therapeutic Chemical (ATC) drug class Level 2 and preferred name using the number and percentage of subjects for each treatment group and overall. A subject reporting the same medication more than once will be counted only once when calculating the number and percentage of subjects who received that medication. The summary will be ordered by ATC medical class and preferred term in the order of descending overall frequency. For drugs with the same frequency, sorting will be done alphabetically.

For the purposes of analysis, any medication with a start date/time prior to the first dosing date/time of study drug will be included in the prior medication summary regardless of when the stop date/time is. If a partial start date/time is entered the medication will be considered prior medications unless the month and year (if day is missing) or year (if day and month are missing) of the start date are after the first dosing date. Medications with a completely missing start date will be included in the prior medication summary, unless otherwise specified.

Summaries will be based on the Safety Population. No formal statistical testing is planned.

Specific by-subject listing of prior medications (antibacterial and others) will be provided by subject ID number in ascending order.

